6.11.5. Analyses of Exploratory Efficacy and Health Outcomes Objectives

An MMRM model similar to that for the primary endpoint will be used to analyze actual and change from baseline in pump factors that affect insulin dosing. The pump factors including carbohydrate ratio (CR), active insulin time (AIT), and insulin sensitivity factor (ISF) will be captured in eCRF throughout the study. A listing of pump factors will be provided including data collected at Visit 2 and the changes captured. Actual and change from baseline in these pump factors will be summarized between LY900014 and Humalog using an MMRM model as specified in Section 6.11. The frequency of bolus type (normal, square or dual wave) used will be collected at Visit 4 and Visit 13 as another pump factor. The frequency of use of non-normal bolus type (square or dual wave), will be summarized and compared between LY900014 and Humalog using an ANCOVA model specified in Section 6.11.

For the Insulin Treatment Satisfaction Questionnaire (ITSQ), the change from baseline to LOCF endpoint while on treatment in each domain transformed score (inconvenience, lifestyle, hypoglycemic control, glycemic control, delivery system) and overall transformed score will be analyzed using the ANCOVA model with strata (pooled country, HbA1c stratum ($\leq 7.5\%$, $> 7.5\%$), and patient's personal CGM or FGM use during the study), and treatment as fixed effects and baseline as a covariate.

Summary statistics, including number of patients and proportion of categorical outcomes (5 levels) for the 5 dimensions (mobility, self-care, usual activity, pain/discomfort, and anxiety/depression) of the European Quality of Life – 5 Dimensions 5 Level (EQ-5D-5L) will be provided by visit and by treatment. The change from baseline to LOCF endpoint (Week 16, Visit 13) in the EQ-5D-5L United Kingdom (UK) population-based health state index score and

EuroQol visual analog scale (EQ-VAS) score will be analyzed using the ANCOVA model with terms same as those for ITSQ analysis.

The proportions of patients with HbA1c <8%, ≤8%, <9% and ≤9% at baseline, Week 16 and LOCF endpoint will be summarized by treatment.

Within-day and between-day glycemic variability measured by the SD and the coefficient of variation (CV) of 10-point SMBG profiles will also be analyzed by the MMRM model specified in Section 6.11.4. At a given visit, the CV and SD on each day with a valid SMBG profile will be calculated using all the glucose values within that day, then the average values of these CVs and SDs will be used as the within-day CV and SD at that visit in analysis. At a given visit, the CV and SD at each of the 10 pre-specified SMBG time points will be calculated using the corresponding glucose values of the valid SMBG profiles, then the average values of these CVs and SDs will be used as the between-day CV and SD at that visit in analysis.

The 1-hour and 2-hour PPG excursions by 10-point SMBG profile and daily average of the 10-point SMBG profile will be analyzed similarly.

The following additional variables from the MMTT will be analyzed using the ANCOVA model described in Section 6.11.2:

- Incremental areas under the serum glucose concentration-time curve (iAUC) from 0 to 30 minutes, 0 to 1 hour, 0 to 2 hours, 0 to 3 hours, and 0 to 4 hours after the meal in MMTT. iAUC is the total area under the serum glucose curve but above the glucose level at time 0 (average of measurements at time -15 and 0) when the meal starts for the MMTT within the specific time frame. The area will be calculated by trapezoids rule.
- Area under/above the serum glucose concentration time curve from 0 to 30 minutes, 0 to 1 hour, 0 to 2 hours, 0 to 3 hours, and 0 to 4 hours after the meal in MMTT.
 - AUC: Total area under the serum glucose curve calculated by trapezoids area within the specific time frame
 - AUC>180: Total area under the serum glucose curve but above the 180 mg/dL level within the specific time frame
 - AUC≤70: Total area above the serum glucose curve but below the 70 mg/dL level within the specific time frame.
- Glucose variability during MMTT (CV and SD of all serum glucose values collected during the MMTT).

The incidence of patients with HbA1c <7.0% and ≤6.5% at Week 16 (Visit 13), imputed using LOCF, and no severe hypoglycemia during 16 weeks of treatment will be compared using a logistic regression model with terms for treatment and baseline HbA1c value.

In addition, CGM outcomes that are not included in the secondary efficacy endpoints will be analyzed as exploratory efficacy endpoints. Details for the CGM analyses can be found in Section 6.13.

6.12. Safety Analyses

Safety measures will include AEs, hypoglycemia, unplanned infusion set changes and reasons, vital signs and weight, treatment exposure, laboratory measures, and antibodies to insulin lispro.

Continuous safety variables, as well as the change from baseline for these variables, will be analyzed either by MMRM or ANCOVA models. For categorical variables, Fisher's exact test or Pearson's chi-square test will be used to compare treatment groups unless otherwise specified.

6.12.1. Extent of Exposure

Duration of exposure to study drug will be summarized based upon eCRF data. The following summary statistics will be provided: n, mean, SD, median, minimum, maximum, and sum (that is, total patient-years of exposure). The number and proportion of patients falling into the following different exposure categories will also be summarized: <4 weeks (>0 and <28 days), ≥ 4 and <8 weeks (≥ 28 and <56 days), ≥ 8 and <12 weeks (≥ 56 and <84 days), ≥ 12 and <16 weeks (≥ 84 and <112 days) and ≥ 16 weeks (≥ 112 days).

Patients who complete the study treatment period are required to complete a safety follow-up visit without study drug; and patients who discontinue the IP prematurely are encouraged to remain in the study without study drug. The days on study after discontinuing IP, and the days on study from date of first study drug to the last study visit date up to Visit 801 will also be summarized.

6.12.2. Adverse Events

Events that are newly reported after the first dose of IP or reported to worsen in severity from baseline will be considered treatment-emergent adverse events (TEAEs). The MedDRA lowest level term (LLT) will be used in the treatment-emergent assessment. The maximum severity for each LLT during the baseline period will be used as baseline severity. For events occurring on the day of first dose of blinded insulin provided by this study, the case report form (CRF)-collected flag will be used to determine whether the event started or worsened post-treatment.

Serious adverse events (SAEs), AEs reported as reason for discontinuation from the IP or study, and TEAEs will be summarized in tables using the MedDRA PT, sorted by decreasing frequency within the LY900014 treatment group. Treatment-emergent adverse events will also be summarized by PT sorted by decreasing frequency within SOC for all TEAEs and by maximum severity. For events that are specific to only one sex, the denominator and computation of the percentage will include only patients from the given sex. The number and proportion of patients with at least 1 event for each type of event will be summarized and compared between treatment groups using Fisher's exact test. Serious adverse events, AEs reported as reason for discontinuation from the study, and TEAEs will also be summarized for open-label Humalog during the lead-in period.

6.12.3. Hypoglycemic Events and Other Adverse Events

6.12.3.1. Hypoglycemic Events

Hypoglycemia events that occur during the study will be captured using a paper diary starting from Visit 2 through Visit 801. Whenever hypoglycemia is suspected ($BG \leq 70 \text{ mg/dL}$ [3.9 mmol/L]), the patient should record the BG value, any associated symptoms, and the treatment administered. A set of events is counted as 1 event in analysis if the duration between adjacent events is ≤ 30 minutes.

The event with the highest severity will be selected for analysis with severity determined in the order of: 1) it is a severe hypoglycemia, 2) it has symptoms of hypoglycemia reported, and 3) it has the lowest blood glucose value. If there are multiple events tied in all 3 aspects, the event with the largest number of non-missing responses to the questions of nocturnal hypoglycemia and postmeal time frame will be selected. Hypoglycemia rates will be summarized for periods of 1 year and 100 years (severe hypoglycemia only). The rate of severe hypoglycemia per 100 years will be compared between treatment groups using the empirical method (see [Appendix 1](#) for details). For each of other categories of hypoglycemia, the number of hypoglycemia events during 0 to 16 weeks (rate) after randomization will be analyzed by using a negative binomial regression model including treatment. An offset defined as the log transformation of treatment exposure in the specific period (days)/365.25 days will be included in the model to estimate the rate of hypoglycemia per year. The proportion of patients with at least 1 hypoglycemic event in each category (incidence) during 0 to 16 weeks after randomization will be analyzed using a logistic regression model including treatment.

The following types of hypoglycemia events will be derived in the analysis data sets: documented hypoglycemia, severe hypoglycemia, nocturnal hypoglycemia, and non-nocturnal (daytime) hypoglycemia. Only severe hypoglycemia will be collected as AEs and all episodes of severe hypoglycemia will be considered as SAEs. Documented hypoglycemia will be based on $BG \leq 70 \text{ mg/dL}$ and $BG < 54 \text{ mg/dL}$.

[Table ITRO 6.3](#) provides detailed statistical methods for each endpoint related to hypoglycemia. For these analyses, hypoglycemia events prior to the discontinuation (i.e., last dose) of IP will be summarized. Additional analyses for other types of hypoglycemic events not mentioned in the table may be conducted as needed.

A listing of patients with at least 1 severe hypoglycemia reported (as SAE) after randomization (including Visit 801) will be provided.

A list of MedDRA PTs will be used for the narrow search of potential severe hypoglycemia in spontaneously reported AEs. The events identified through the search strategy that are also reported as SAEs will be summarized and compared between treatments. Fisher's exact test will be used to assess the treatment difference in the proportion of patients with potential severe hypoglycemia.

Table ITRO 6.3. Summary of Analyses for Endpoints Related to Hypoglycemia

Endpoint	Analysis Period ^b	Statistical Method
Rate of hypoglycemic events (per patient per year) 
 • All Documented^a • Nocturnal^a • Non-Nocturnal (or Daytime) (Documented and between waking and bedtime)^a 	0-16 weeks	Negative binomial regression with treatment and log (exposure/365.25 days) as the offset in the model.
Incidence of hypoglycemic events 
 • All Documented^a • Nocturnal^a • Non-Nocturnal (or Daytime) (Documented and between waking and bedtime)^a 	0-16 weeks	Logistic regression with treatment
Rate of post-meal hypoglycemic events (per patient per year) 
 • All Documented^a 	$\leq 1, \leq 2, \leq 4$, and >2 to ≤ 4 , and >4 hours after start of a meal within 0-16 weeks	Negative binomial regression with treatment and log (exposure/365.25 days) as the offset in the model.
Incidence of post-meal hypoglycemic events 
 • All Documented^a 	$\leq 1, \leq 2, \leq 4$, and >2 to ≤ 4 , and >4 hours after start of a meal within 0-16 weeks	Logistic regression with treatment
Rate of severe hypoglycemic events (per patient per 100 years)	0-16 weeks	Exposure adjusted rate per 100 years (calculated by total number of events divided by total exposure for individual patients) will be provided and the empirical method (see Appendix 1 for details) will be used for treatment comparison.
Incidence of severe hypoglycemic events	0-16 weeks	The treatment comparison will be based on a logistic regression model with treatment as a covariate.

^a All documented hypoglycemia and the subcategories based on the thresholds of BG ≤ 70 mg/dL and BG < 54 mg/dL will be analyzed.

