5.5 Justification for Dose

The basal and bolus delivery of insulin will be determined based on the individual needs of each patient. LY900014 has the same insulin lispro concentration (100 U/mL) as that of commercially available Humalog. At the randomization visit, IP may be substituted for Humalog (used during lead-in) on a unit-for-unit basis. The addition of treprostinil to the

Humalog formulation does not modify the physical, chemical, or biological integrity of Humalog. Furthermore, the total glucose-lowering effect during euglycemic clamp experiments is similar between LY900014 and Humalog. Nevertheless, improved postprandial glucose values were observed with LY900014 after test meals, which may potentially increase the risk for early postprandial hypoglycemia with LY900014.

6. Study Population

Patients must give written informed consent (approved by Eli Lilly and Company [Lilly] or its designee and the ethical review board [ERB] governing the site) before being allowed to participate in the study and before any screening assessments are performed.

Study investigator(s) will review the patient's records and/or history and screening test results/measurements to determine if the patient meets all inclusion and no exclusion criteria to qualify for participation in the study. All screening activities must be completed and reviewed before the patient begins the lead-in period.

Prospective approval of protocol deviations to recruitment and enrollment criteria, also known as protocol waivers or exemptions, are not permitted.

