9.4. Safety

9.4.1. Hypoglycemia

Patients will be required to perform SMBG when hypoglycemia is suspected through

- symptoms experienced,
- personal CGM or FGM readings, or
- a perceived increased risk as related to
 - dietary intake,
 - physical activity, or
 - inadvertent or atypical insulin dosing.

All patients will be instructed to treat a BG ≤ 70 mg/dL (3.9 mmol/L) as hypoglycemia.

If a hypoglycemia event is suspected, the patient should record the BG value, any associated symptoms, and the treatment administered in the study diary. The patient should contact the site as necessary. All hypoglycemia events (severe and nonsevere) must be reported on the hypoglycemia eCRF. All episodes of severe hypoglycemia must be confirmed by the investigator and then reported as SAEs on the AE eCRF page and on the SAE eCRF page. Episodes of hypoglycemia not meeting the criteria for severe hypoglycemia should not be reported as an AE.

Hypoglycemia will be described using the following definitions:

- **Documented Glucose Alert; BG ≤ 70 mg/dL (3.9 mmol/L):**
 - Documented symptomatic hypoglycemia: an event with typical symptoms of hypoglycemia.
 - Documented asymptomatic hypoglycemia: an event without typical symptoms of hypoglycemia.
 - Documented unspecified hypoglycemia: with no information about symptoms of hypoglycemia available (this has also been called unclassifiable hypoglycemia).
- **Documented Clinically Significant Hypoglycemia with similar criterion as above except for threshold BG < 54 mg/dL (3.0 mmol/L)**
 - Documented symptomatic hypoglycemia

- Documented asymptomatic hypoglycemia
- Documented unspecified hypoglycemia
- **Probable Symptomatic Hypoglycemia:** an event during which symptoms are present, but BG measurement was not reported.
- **Severe Hypoglycemia:** during these episodes, patients have an altered mental status and cannot assist in their own care, may be semiconscious or unconscious, or experience coma with or without seizures, and the event requiring assistance of another person to actively administer carbohydrate, glucagon, or other resuscitative actions. Blood glucose measurements may not be available during such an event, but neurological recovery attributable to the restoration of BG concentration to normal is considered sufficient evidence that the event was induced by a low BG concentration (BG ≤ 70 mg/dL [3.9 mmol/L]).
- **Other Hypoglycemia**

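### The 30-minute merge of hypoglycemia diary entries ranks symptoms above glucose, so some episodes with a reading <54 mg/dL leave the <54 mg/dL count

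*SAP*

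**What the plan says.** SAP 6.12.3.1 merges entries whose gap is no more than 30 minutes: "A set of events is counted as 1 event in analysis if the duration between adjacent events is" within that limit. One entry then stands for the whole set. Severe status ranks first; after that the SAP lists "2) it has symptoms of hypoglycemia reported, and 3) it has the lowest blood glucose value". Glucose is thus the third criterion. Entries still tied are separated by how fully the nocturnal and postmeal questions were answered.

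The same section bases documented hypoglycemia on BG ≤70 and <54 mg/dL. Footnote a to SAP Table ITRO 6.3 applies both cut-offs to the analyses ("All documented hypoglycemia and the subcategories based on the thresholds of BG"). They cover rate (negative binomial) and incidence (logistic), including the nocturnal, daytime and postmeal breakdowns.

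Protocol 9.4.1 labels BG <54 mg/dL as clinically significant. It also defines documented events without symptoms, and probable symptomatic hypoglycemia, which is "an event during which symptoms are present, but BG measurement was not reported". It accepts that a severe event may have no BG.

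**The concern.** The selection key does not match the outcome it feeds. Glucose decides between entries only when they tie on severe status and on symptoms, yet glucose defines the categories that are counted. Neither document says that the lowest BG of the set is retained, that the <54 flag is set before merging, or that merging is done separately for each threshold. SAP 6.12.3.1 also does not say how a missing BG ranks on the third criterion. Because the gap is measured between adjacent entries, a chain lasting longer than 30 minutes in total also collapses to one entry.

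At stake are the diary counts behind other secondary objectives 8 (postmeal) and 9 (all documented), at the threshold the protocol treats as clinically significant. The error runs one way, towards fewer events.

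**Working it through.** The documents state no figure that depends on this rule, so there is none to reproduce. The check applies the rule as written.

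**Single sets.** Each pair lies within 30 minutes.

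| Entries in the set | Entry kept | Lowest BG in set | Effect |
|---|---|---|---|
| Symptomatic 65; asymptomatic 50 | 65 | 50 | Leaves <54 count; stays in ≤70 |
| Symptomatic, no BG; asymptomatic 50 | No BG | 50 | Leaves both documented counts |
| Severe, no BG; symptomatic 50 | Severe, no BG | 50 | Leaves <54 count; stays in severe analyses |
| Symptomatic 65; symptomatic 50 | 50 | 50 | No loss |

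**Direction.** The BG of the kept entry is never below the lowest BG in the set, and may be missing. The rule can therefore remove a set from the <54 count but cannot add one.

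**Enumeration.** All unordered two-entry sets were formed from severe (yes/no), symptoms (yes/no/unknown) and BG (missing, 48, 53, 54, 60, 70 mg/dL). A non-severe entry without a BG was allowed only if symptomatic. Unknown symptoms were treated as not reported, and a missing BG was ranked last.
- Sets with a reading <54: 342. Lost from the <54 count: 104 = 78 (kept entry 54-70 mg/dL) + 26 (kept entry without BG).
- In 88 of the 104 (66 + 22) the kept entry is severe. Among sets with no severe entry, 16 of 81 are lost (12 + 4).
- Sets with a reading ≤70: 585. Kept as an entry without BG: 65, of which 55 are severe and 10 are non-severe.

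These are counts of logical combinations, not expected frequencies. The grid greatly over-represents severe entries. With the threshold set from the lowest BG, none of the 342 is lost.

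**Size.** A <54 event recorded as a single entry cannot be lost, so

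undercount of the <54 rate = q × d,

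where q is the share of <54 events lying in merged sets and d is the share of those outranked by an entry that is not <54. The documents give neither. The assumed ranges are q = 2-20% and d = 10-50%.
- Low end: 0.02 × 0.10 = 0.002, or 0.2%.
- High end: 0.20 × 0.50 = 0.10, or 10%.

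**Effect on a comparison.** Reported ratio = true ratio × (1 − q·d on LY900014)/(1 − q·d on Humalog). If the product is equal in the two arms, the ratio is unchanged and both rates are low. For illustration, take q = 20% in both arms and a true ratio of 1.30:
- d = 10% on Humalog and 20% on LY900014: 1.30 × 0.96/0.98 = 1.27.
- d = 5% on Humalog and 20% on LY900014: 1.30 × 0.96/0.99 = 1.26.

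**The case against.** **The pattern may be uncommon.** A loss between two non-severe entries needs a symptomatic entry that is not <54 and, within 30 minutes, a separate <54 entry without reported symptoms. If symptoms are recorded on both, the lower BG is kept. Hypoglycemia unawareness as judged by the investigator is an exclusion. SMBG is required when hypoglycemia is suspected, and neither document says that rechecks are filed as separate events. This stands as a limit on size. It does not remove the mechanism, because the protocol defines asymptomatic events and symptomatic events without a BG.

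**The order follows a protocol classifier.** Protocol 9.4.1 divides both BG thresholds by symptoms, and the SAP's own order treats a symptomatic entry as the more severe one. It is fair to say that the kept entry is milder only on the glucose scale. Set-level flags would still preserve symptom status without giving up the lowest BG.

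**Severe events are not hidden.** They have their own rate and incidence analyses, a listing, SAE reporting and narratives. Protocol 9.4.1 accepts neurological recovery as evidence of a low BG and treats severe events as special cases of documented or probable hypoglycemia. For a severe entry without a BG, the clear loss is therefore from the <54 count; loss from the ≤70 count is arguable.

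**Blinded CGM covers <54 mg/dL separately.** That is true, including postmeal windows, and the diary merge cannot affect it. It covers only the CGM sessions and does not correct the diary counts.

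**A tempting stronger reading.** A reader might infer that the rule hides a safety signal for LY900014, since Protocol 5.5 notes improved postprandial glucose "which may potentially increase the risk for early postprandial hypoglycemia with LY900014". The documents do not support that inference. More early events on one arm does not mean that a larger share of them is outranked, and the trial is double-blind with the same diary in both arms.

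**Conclusion.** The rule as written is wrong for categories defined by glucose. Followed exactly, it drops some <54 mg/dL episodes and never adds any. Non-severe sets kept without a BG also drop out of the ≤70 count.

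The undercount of the <54 rate is about 0.2-10% under assumed inputs, and it may well be small. Incidence changes only for a patient with no other counted <54 event. A difference between arms is possible but not shown, so the rate ratios in the working show sensitivity and are not estimates. The affected endpoints are other secondary objectives without multiplicity control. The primary objective is untouched. The correction is worth making because the error has one direction, lies in a safety count, and is cheap to remove.

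**What to change.** In SAP 6.12.3.1, keep the 30-minute merge but classify the merged set rather than one selected entry:
- Set the ≤70 and <54 mg/dL flags from the lowest non-missing BG in the set.
- Record severe as yes if any entry is severe, and symptoms as yes if any entry reports them. If symptom subcategories are tabulated, state that the symptom flag belongs to the set, since the lowest BG and the symptoms may come from different entries.
- Take the nocturnal and postmeal flags from entries with non-missing answers, and state which prevails if answered entries disagree. Taking them automatically from the first entry could discard a postmeal answer given later and remove the set from objective 8; the SAP's existing tie-break already favours answered entries.

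The cost is one SAP paragraph and a minor programming change before unblinding, with no new data. The <54 mg/dL counts would be slightly higher. Double counting stays prevented, and no severe or symptom classification is lost.
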